## PARTICIPANT RECRUITMENT

### 12. INCLUSION CRITERIA

1. People aged between 18 years to 75 years diagnosed with TIA or first-ever minor stroke (excluding subarachnoid haemorrhage (SAH)) (National Institutes of Health Stroke Scale (NIHSS) score  $\leq$  4) and/or modified Rankin Scale (mRS) score 0-2 at discharge [1] in the past 6 weeks

2. Admitted to one of the three Auckland based hospitals or identified via primary care for minor stroke or TIA
3. Who can converse in English
4. Provides written informed consent
5. Exclusion criteria
6. History of major stroke or myocardial infarction (verified through Clinical Portal medical records)
7. Planned carotid endarterectomy
8. Life-threatening conditions with a life-expectancy <5 years
9. Current (in the past year) significant clinical depression/anxiety (Hospital Anxiety and Depression questionnaire (HADS)  $\leq 11$  in either or both the depression and anxiety domains) (either in clinical records or at screening) OR psychiatric conditions (based on medical records),
10. History (past year) of alcohol or drug/substance abuse
11. Dependent on others (living in a rest-home/care facility)
12. Significant cognitive impairment or pre-existing diagnosis of dementia e.g. ACE-R  $\leq 82$  (from clinical records), or at screening (MoCA (<26))
13. Participation in another RCT

The majority of the inclusion and exclusion criteria will be determined by means of medical record/clinical portal screening, completed by hospital based research staff. If all the relevant information is not available, the initial section of the Baseline assessment will allow further screening to check for remaining criteria (e.g. cognitive impairment or abnormal mood). Exclusion due to significant anxiety and depression [58, 59] or cognitive impairment [60] are necessary in order to recruit participants who will be able to engage effectively with the study over a period of 12 months.

---

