## Hospital Anxiety and Depression Scale (HADS)

The HADS is a commonly used scale to identify anxiety and depression disorders, including stroke and TIA patients [65-67]. The scale has seven items for depression and seven items for anxiety, with a total possible score of 0-21 for each, with 0-7 being = normal, 8-10 – borderline abnormal, and 11-21 = abnormal. As part of the screening for TIIPS, those who score ≥11 on either the depression or anxiety items will not be eligible to participate in the trial.

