### *Confirmation of non-medical inclusion & exclusion criteria:*

Participants that have proceeded to this stage will have met the cut-off for blood pressure score.

Following this, the Research Assistant will use a hard copy of the MoCA© and enter results directly into the REDCap form. This will calculate total score. If participant scores <26 they will need to be excluded. The Research Assistant performing the MoCA© should complete the online MoCA© Training and Certification Program at <https://www.mocatest.org/>.

If the inclusion criteria are met, the participant will proceed to complete the Hospital Anxiety and Depression (HADS) questionnaire. If the score for HADS is greater than 11 in either the Anxiety or Depression domains, the participant is ineligible to continue.

If participants are ineligible at this stage they will be notified of not meeting the study requirements and thanked for their interest in the study. They should be offered reimbursement for their time, if requested, in line with local ethics approvals.

The RAs conducting the assessments will be provided with the study Manual of Procedures, outlining all the day to day processes for conducting the study, safety information, contact details of senior study staff, as well as a field manual for easy reference. They will also be provided with iPads for data entry, mobile phones and stationary for data collection and record keeping.

---

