1.16. Planned carotid endarterectomy  Yes  No

1.17. Life-threatening conditions with a life expectancy  $<$  5 years  Yes  No

1.18. Significant co-morbidities (pre-stroke/TIA mRS >2)  Yes  No

1.19. Current (in the past year) significant clinical depression/anxiety either in clinical records or at screening) or psychiatric conditions (based on medical records)  Yes  No  Unknown  
((If unknown, check unknown, to be completed by RA at Baseline screening).)

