8.15. Anxiety Score (Sub Total)

(Advise the participant and study manager to contact GP if the score is equal to or more than 11.)

---

Anxiety warning

---

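### The HADS exclusion in section 12 runs opposite to its own label and to the protocol's scale, and the two other HADS rules disagree at a score of exactly 11

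*Protocol*

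**What the plan says.** The protocol sets a HADS eligibility rule in three places, and Form B touches on it in two more.

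- **Section 12, exclusion list, item 9.** The exclusion for current significant depression or anxiety is defined as "Hospital Anxiety and Depression questionnaire (HADS) $\leq 11$ in either or both the depression and anxiety domains". The paragraph after the list gives the purpose, which begins "Exclusion due to significant anxiety and depression", and explains that participants must be able to engage with a 12-month study.
- **Assessment information, HADS section.** Each domain is scored 0 to 21 and banded as "0-7 being = normal, 8-10 – borderline abnormal, and 11-21 = abnormal". The trial rule follows: "those who score ≥11 on either the depression or anxiety items will not be eligible to participate in the trial".
- **Appendix A, confirmation of non-medical criteria.** This is the procedure for the research assistant at baseline: "If the score for HADS is greater than 11 in either the Anxiety or Depression domains, the participant is ineligible to continue".
- **Form B, item 1.19.** The exclusion is worded as "significant clinical depression/anxiety either in clinical records or at screening", with no HADS value. Unknown cases are left for the research assistant to complete at baseline screening. The block ends with an instruction that any yes makes the person ineligible.
- **Form B, items 8.15 and 8.16.** The anxiety and depression score fields show a warning and the advice to "contact GP if the score is equal to or more than 11". Neither mentions eligibility.

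**The concern.** A cut-off that excludes low scores cannot identify significant depression or anxiety on a scale where 11 to 21 is the abnormal band. The criterion in the governing list therefore contradicts its own label, the rationale printed below it and the scale defined later in the protocol.

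Correcting the direction does not settle the rule. The two passages that run the other way use different boundaries, at or above 11 and strictly above 11. A person scoring exactly 11, which the protocol calls abnormal, is ineligible under one and eligible under the other.

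What is at stake is consistent eligibility decisions and a usable reference for violations. The Protocol Violations section gives wrongly included ineligible participants as an example of a violation, and section 34 plans a per-protocol analysis beside the intention-to-treat analysis. If the governing criterion is one that every participant admitted on HADS under the other two passages fails, neither has a sound basis. Mood is also a secondary aim, and HADS is repeated at follow-up, so the threshold sets the baseline range of an outcome.

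**Working it through.** The protocol states no figure to reproduce here. The check applies the three rules literally to every possible score.

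**Inputs.** Anxiety and depression are each scored 0 to 21, which is 22 values per domain, and higher is worse (HADS section). The rules are:

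- Section 12: exclude if either domain is ≤ 11.
- HADS section: exclude if either domain is ≥ 11.
- Appendix A: exclude if either domain is > 11.

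**All score pairs.** 22 × 22 = 484.

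**Pairs left eligible on HADS.** Each rule excludes on either domain, so both domains must fall in the permitted range.

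| Rule | Permitted range, both domains | Values per domain | Eligible pairs |
|---|---|---|---|
| Section 12, literal | 12–21 | 10 | 10 × 10 = 100 |
| HADS section | 0–10 | 11 | 11 × 11 = 121 |
| Appendix A | 0–11 | 12 | 12 × 12 = 144 |

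**Overlap.** The range 12–21 shares no value with 0–10 or 0–11. Section 12 therefore has 0 eligible pairs in common with either other rule.

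**Boundary disagreement.** The HADS section's pairs all lie within Appendix A's, so the two differ on 144 − 121 = 23 pairs. These have exactly 11 on at least one domain and nothing above 11.

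**Normal on both domains (0–7).** There are 8 × 8 = 64 such pairs. Section 12 excludes all 64, and the other two rules admit all 64.

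**Abnormal on at least one domain (11 or more).** There are 484 − 121 = 363 such pairs. The literal section 12 rule admits 100 of them and still excludes 363 − 100 = 263, because a score of 11 or less on the other domain is enough to exclude.

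**Illustrative participants** (anxiety, depression):

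| Scores | Section 12 | HADS section | Appendix A |
|---|---|---|---|
| 5, 5 | ineligible | eligible | eligible |
| 11, 4 | ineligible | ineligible | eligible |
| 14, 4 | ineligible | ineligible | ineligible |
| 14, 14 | eligible | ineligible | ineligible |

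**Form B.** Item 1.19 and the closing instruction of its block do stop a person with depression or anxiety, but the research assistant completing an unknown case finds no number there. The number 11 appears at the score fields, where it prompts only a warning and GP advice. By contrast, the MoCA total field (item 7.1.8) states ineligibility at 25 or below and tells the assessor to stop, and the average systolic pressure field (item 15A.7) states ineligibility below 130. HADS has no such numeric stop where it is scored, so the form does not settle which of the three rules applies.

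**The case against.** The strongest reply is that nobody would follow section 12 literally. Its label, its rationale, the HADS section and the Appendix A procedure all point to excluding high scores. This looks like a sign error, and the working ambiguity is confined to one score, exactly 11. That is largely right. A reader might infer that the trial would recruit the opposite population; the documents do not support this, because the procedure staff are given runs the other way.

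Three other stronger readings also fail:

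- One might say that the literal rule admits people with depression or anxiety. It admits only those scoring 12 or more on both domains. The same item also excludes on clinical records and psychiatric conditions.
- One might say that Form B has no stop. It has one at item 1.19. What is missing is a numeric cut-off there and a stop at the HADS score fields.
- One might say that more than half the scale, hence more than half the patients, is excluded. Scale values are not people, and no score distribution is given.

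It can also be said that screening comes before randomisation, so an error at this step falls on both arms alike. It does not bear on the systolic pressure endpoint, alpha or the power calculation. That stands.

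Finally, the inequality sign was read from a PDF and could have been misread. The other inequalities in the same list (NIHSS, ACE-R, MoCA) read sensibly, so there is no sign of a general fault. The conflict between the HADS section and Appendix A does not depend on that sign, since Appendix A states its rule in words.

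**Conclusion.** The point holds as an internal contradiction in an eligibility criterion. Section 12 is wrong in direction against the protocol's own label, rationale and scale, and the remaining two rules disagree at exactly 11.

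The practical exposure is twofold. Participants scoring exactly 11 on a domain, with nothing above 11, may be handled differently depending on which passage is followed. And everyone eligible on HADS under the HADS section or Appendix A formally meets the section 12 exclusion, which undermines violation reporting. How far this carries into the per-protocol analysis depends on whether eligibility breaches remove participants from that set, which the protocol does not state.

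The conclusion assumes that the printed inequality in section 12 is the one in the source document. If it is not, the first defect falls away and the boundary conflict at 11 remains. The number of patients affected cannot be estimated from the document, and no sample-size or power figure changes.

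**What to change.** Reconcile five places to one HADS rule with the same direction and a single boundary: section 12 item 9, the HADS section, Appendix A, Form B item 1.19 and Form B items 8.15 and 8.16. Which boundary to adopt is for the investigators. Put the chosen value into item 1.19, and tie an eligibility stop to it at the baseline HADS score fields, as is already done for MoCA. Keep the GP advice as a separate prompt, so that a safety action is not mistaken for an eligibility rule.

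If recruitment has begun, record which rule was applied in practice and list any participant with a score of exactly 11, so that violations are judged against one stated criterion.

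The cost is a short text correction in the protocol and a validation rule in REDCap. Sample size, endpoint and analysis model are unaffected.

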## 13. SCREENING

[figure not shown]
Screening will happen in two stages (see Flowchart Figure 1).

Potential participants initially screened for eligibility based on the study inclusion and exclusion criteria (See **Appendix C** Case Record Forms, Screening Form) from hospital admission information at the public hospitals in Auckland. Those deemed to be potentially suitable will be contacted by a hospital-based research assistant to briefly explain the study and for verbal consent to be contacted by a study research assistant.

Those who agree to be contacted will be telephoned by a study research assistant (RA). The RA will provide a brief description of the study, and the screening form will be reviewed to confirm eligibility based available information. If a person is found to be ineligible, the reason will be explained and the participant thanked for their interest in participating in the trial.

14. STUDY PROCESSES FLOWCHART

## STUDY PROCESSES

---

### 15. RECRUITMENT SITES

1. Auckland City Hospital, Grafton, Auckland City
2. Middlemore Hospital, Otahuhu, Auckland
3. Northshore Hospital, Takapuna, Auckland
4. Waitakere Hospital, Henderson, Auckland
5. GP clinics, Auckland Supercity

---

### 16. PARTICIPANT RECRUITMENT PROCEDURES

Trial participants will predominantly be recruited through hospital referrals. Hospital based RAs (HRA) based in the stroke wards and HRAs who have access to the Clinical portal and patient medical records will conduct daily searches of presentations and admissions to hospital with any diagnoses suggestive of stroke and/or TIA. For those patients with a diagnosis of stroke or TIA as confirmed by their treating physician, the RA will further search their records for the main eligibility criteria as listed in section 2.1. Those who meet the criteria will be approached either in-person if still in hospital or by telephone if discharged, by the HRA, for verbal consent to be contacted by a study RA for further information about the study. The HRA will provide the name and contact details (usually a landline or mobile number) of those who agree to be contacted to the community RA (CRA). The number of people who meet the initial screening criteria will be registered in the study database. Potential participants who are identified through GP practices will be approached by the GP or clinic nurse for verbal consent to approach the patient for their interest in the study. Those who consent to be contacted will be telephoned by a CRA in a similar manner as for hospital referrals. Confirmation of TIA/stroke diagnoses will be conducted by checking medical records and/or by the study neurologists.

---

### 17. CONSENTING

The CRA will contact those who have provide verbal consent for initial contact, will be telephoned by a CRA to explain the study in detail and to answer any questions. Participants will be informed of their choice to participate and to withdraw at any time, will have a chance to ask any questions. Following this, those who agree to participate will be asked to send a signed copy of the PISC to the research team via post, e-mail or electronic scanning (e-consent). The signed consent form will be

countersigned by a research assistant as the person who explained the study to the participant. A copy of the signed consent form will be retained by the study participant, and an e-copy will be retained by the study team in the REDCap database. Eligible participants will be registered on the TIIPS REDCap database and assigned a unique participant ID.

---

## 18. ASSESSMENTS

There will be a total of five assessments: baseline, 3, 6, 9 and 12 months. Eligible participants will be contacted by CRAs to book appointments for assessments. The baseline and 6-month assessments will be conducted face to face to allow the measurement of the primary outcome metrics for the LS7 (height, weight, blood pressure, blood glucose and blood cholesterol) as well as cognitive assessments. The 3-, 9- and 12-months assessments will be conducted over telephone, at a suitable time.

For face-to-face assessments, the participant will have the option of attending a clinic at one of the three locations at the AUT campuses (AUT North, City or South). Participants travelling to clinics will be provided a petrol or supermarket voucher (NZ \$20) for parking or travel costs.

Participants who are unable to travel to clinic sites will be offered a home visit to conduct the baseline and 6-month assessments.

---

## 19. COVID-19 OUTBREAK RELATED RESTRICTIONS

The research Protocol may need to be amended should there be a COVID outbreak and government-imposed restrictions. The pandemic may result in the reduced ability to recruit participants, and conduct face to face assessments. The trial will follow the NZ government guidelines and AUT policies. The ethics committees will be informed of any significant changes and approvals for amendments will be sought as required.

### **COVID-10 Protection Framework Requirements**

Research guidelines at AUT at the Red level of the Protection Framework are outlines at the weblink <https://auti.aut.ac.nz/resch/duringcovid-19/Pages/default.aspx>. All RAs who will be contacting participants in-person will be required to be fully vaccinated against COVID-19, and will

be required to wear medical masks during all in-person assessments. Gloves and eye protection will be worn during blood sample collection.

### 3.5 CASE RECORD FORMS AND QUESTIONNAIRES

#### 20. LIST OF QUESTIONNAIRES

Table 1. List of outcome measures

Outcome measure	Baseline	3	6	12
Demographic Factors: Age, sex, ethnicity, employment, education, marital status	✓			
Event type - stroke and pathological subtypes, or TIA and event date (physician diagnosed)	✓			
Hospitalization details: hospital, date of admission, date of discharge	✓			
Event details (revascularization and planned procedures) from medical records	✓			
Hospital Anxiety and Depression Scale	✓	✓	✓	✓
Stroke awareness (recognition of risk factors, knowledge of actions) [61]	✓	✓	✓	✓
Quality of life (EQ-5D-5L) [62]	✓		✓	
Cognitive functioning by MoCA [63]	✓		✓	
Medication adherence and self-efficacy (SEAMS) REF)	✓	✓	✓	✓
Physical measurements (non-fasting blood test, SBP/DBP, BMI, HR)*	✓		✓	
Absolute and relative 5-year risk of stroke (as measured by Stroke Riskometer app)	✓		✓	
Lifestyle factors (Diet score, physical activity, smoking, alcohol)	✓	✓	✓	✓
CVD outcomes, recurrent events, hospitalisation (stroke, CVD events) self-report and/or from clinical records	✓	✓	✓	✓
Health and Service costs: NMDS (NZ)			✓	✓
Productivity level NMDS (NZ)	✓	✓	✓	✓
Participant feedback questionnaire – Intervention group only	✓	✓	✓	✓

Items will include demographic factors, medical history, lifestyle risk factors, awareness of stroke risk factors, warning signs, symptoms and actions;[64] depression screening test (Hospital Anxiety and Depression Scale) health related quality of life ([EQ-5D-5L](#)),[62] health-care resource

use questionnaire, cognitive assessment (Montreal Cognitive Assessment MoCA) and participant satisfaction questionnaires. See 2 for details of measures collected at each timepoint. Life's Simple 7 score will be calculated from corresponding measurements of smoking, BMI, physical activity, healthy diet score, blood total cholesterol, glucose level and BP.[37]

Table 2. Life's Simple 7

Modifiable factors	Poor health	Intermediate health	Ideal health
Smoking status	Current smoker	Former ≤ 12 months	Never or quit > 12 months
Body mass index	≥ 30 kg/m 	25–29.9 kg/m 	< 25 kg/m 
Physical activity	No physical activity	1–3 times, less than 2.5 hours per week	≥ 4 times per week, 2.5 hours or more
Healthy diet score	0–1 component	2–3 components	4–5 components
Total cholesterol	≥ 240 mg/dL	200–239 mg/dL or treated to goal	< 200 mg/dL
Blood pressure	SBP ≥ 140 mm Hg or DBP ≥ 90 mm Hg	SBP 120–139 mm Hg or DBP 80–89 mm Hg or treated to goal	SBP < 120 mm Hg and DBP < 80 mm Hg
Blood glucose	≥ 126 mg/dL	100–125 mg/dL or treated to goal	< 100 mg/dL

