### 2. SECONDARY PREVENTION AFTER TIA/MINOR STROKE

There is ample evidence that modifying health behaviours for stroke and cardiovascular disease (CVD) prevention is feasible, improves health outcomes, reduces healthcare costs, can reduce individual risk of stroke by about 80%.[7][8] and can reduce stroke incidence by about 50%.[9] Addressing health behaviours, including the use of multifactorial lifestyle interventions,[10] can lead to clinically meaningful reductions in CVD and stroke.[11] Both TIA and minor stroke are highly preventable with medical management,[12-14] combined with education about stroke/TIA and the importance of medication adherence and support for lifestyle behaviour change.[15-18] Current NZ stroke guidelines recommend behavioural counselling for diabetes, diet, exercise and smoking cessation for long-term self-management of risk factors.[19] However, in NZ, management of TIA/minor stroke *remains inadequate*. [20] In addition, due to the transient nature of symptoms, *patients do not recognise TIA as a significant medical event* with long-term health implications. Resultant delays in seeking medical treatment, low adherence to healthy lifestyle and prescribed medications, lead to *preventable major secondary events*. [21-23]

---

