### 11. SECONDARY AIMS

The **secondary aims** are to determine the effectiveness of HWC in improving

1. Overall cardiovascular disease (including stroke) risk at 6 months post-randomisation based on the LS7 compared to Baseline

2. Individual LS7 behavioural risk factors at 3-, 6- 9- and 12- months post-randomisation compared to Baseline
3. Awareness about stroke symptoms, risk factors and their management 6- and 12- months post-randomisation compared to Baseline
4. Quality of life, at 6- and 12- months post-randomisation compared to Baseline
5. Cognitive outcomes at 6-, and 12- months post-randomisation compared to Baseline
6. Mood outcomes compared to Baseline
7. Adherence to CVD medications at 3, 6-, and 9 and 12- months compared to Baseline
8. CVD/adverse outcomes at 12 months post randomisation.
9. Health and service costs at 12 months post randomisation
10. Productivity status at 12 months post randomisation

Secondary outcomes are:

1. systolic blood pressure, total cholesterol, blood glucose at 6-months post randomisation
2. change in proportion of participants in 'high' and 'intermediate' to 'low' risk on LS7 at 6-months post randomisation
3. Stroke risk from Stroke Riskometer – 5- year absolute and relative risk at 6- and 12-months post randomisation
4. Quality of life (EQ5D) at 6-months post randomisation
5. Stroke awareness at 6- and 12-months post randomisation
6. Cognitive assessment score (Montreal Cognitive Assessment)
7. Medication adherence (Self-Efficacy For Appropriate Medication Use Scale (SEAMS))
8. CVD adverse outcomes (fatal and nonfatal stroke, TIA, myocardial infarction and heart failure, death attributable to CVD and all-cause mortality)
9. Healthcare and community service costs assessed as self-reported service use questionnaire at follow up. Productivity status will be self-reported and will include items regarding status (e.g., paid work, voluntary work, homemaker, student, unemployed), hours (e.g., full/part time), compared to hospitalisation pre-stroke status.

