## 27. REPORTING AND COMPLIANCE OF INTERVENTION DELIVERY

At the end of each coaching session, coaches will complete the coaching compliance questionnaire on REDCap. This will record when the session took place, the length of the session, the coaches self-rating of how well they judged the session to have gone, and any relevant notes as free text. In addition, a random 10% of interviews will be reviewed by the health coach trainer and given a rating for compliance. If a session was missed, the reasons for this and the plans to make up for this missed session will be recorded.

The intervention will combine educational material and intensive HWC coaching. Participants allocated to the HWC group will have 12 individual coaching sessions over 6 months with trained HWC coaches, of which 4 sessions are carried out weekly, 6 sessions fortnightly and the remaining two sessions monthly. The initial two sessions and the final session will be conducted face-to-face and remaining coaching sessions via telephone. Between the final coaching session and the 12-month assessment, HWC participants will receive a short monthly telephone call from their coach to encourage maintenance of behaviour change. Coaching sessions will take up to 1 hour initially, with later sessions lasting about 30 minutes. IG participants will be provided with tools to assist with behaviour changes.

---

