### 34. INFERENCE ANALYSES

Intention to treat (ITT)[95] analyses and per protocol analysis will be used. To address the primary hypothesis ANCOVA will be used to compare the difference in systolic blood pressure at 6-months post randomisation between the HWC and usual care groups, accounting for baseline stratification factors: (age, gender and ethnicity), referral centres, geographical region and known influential clinical characteristics (e.g., comorbidities). To address the secondary hypotheses linear mixed effects (LME) repeated measures models will be used to investigate the differences in (1) adherence to medication (2) health-related quality of life (3) incidence of new vascular events including death (4) life satisfaction (5) cognition (6) mood) and (7) health service utilisation costs between the HWC and Usual care groups, and by ethnicity (sub-group analysis) at 6-months (plus

life-style and adherence at 1-year post-randomisation. These LMEs will model effect of time (baseline, 3-, 6- 9- and 12-months (medication adherence, lifestyle and awareness at only 12 months), post-randomisation whilst accounting for key demographic stratification factors known to confound with outcomes. Any data not collected within 6-weeks of the follow-up points will be classified as missing data. Baseline covariates of age, sex, most recent blood pressure measure and any additional variables predictive of outcome data will be included in the imputation model.[46] The reasons for missingness and the reasons will be recorded and accounted for. Sensitivity analyses will be conducted to test the assumptions of the model (including a complete case analysis in which only subjects with complete data are included). Familywise error control will be used to account for the multiplicity of tests. Inferences will be based on a 5% significance level and two-sided alternatives.

For the analysis of - CVD adverse outcomes (fatal and nonfatal stroke, TIA, myocardial infarction and heart failure, death attributable to CVD and all-cause mortality), we will use Kaplan-Meier life-test and estimate the hazard ratios (HR) and adjusted HR using time-to-event Cox regression analysis. Time to event analysis will include recurrent events and time-dependant variables where appropriate.

Competing risk method will also be applied to compare the CVD adverse outcomes between the two interventional groups, accounting for mortality outcome.

---

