1.3. Confirmed stroke or TIA by hospital physician  Yes  No  
(Note: A GP is unable to confirm a stroke or TIA)

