**6. Sources of Information related to death**

6.1. NZHIS  Yes  
 No

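### Non-fatal CVD events can be counted on self-report alone, so the secondary event comparison is open to arm-dependent reporting, mainly of TIAs without admission

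*Protocol*

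**What the plan says.** Section 11 names as a secondary outcome "CVD adverse outcomes (fatal and nonfatal stroke, TIA, myocardial infarction and heart failure, death attributable to CVD and all-cause mortality"). Section 34 analyses it between arms: "we will use Kaplan-Meier life-test and estimate the hazard ratios (HR) and adjusted HR using time-to-event Cox regression analysis", with competing-risk methods as well. It adds that "Inferences will be based on a 5% significance level and two-sided alternatives".

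Table 1 (section 20) gives the data source as "CVD outcomes, recurrent events, hospitalisation (stroke, CVD events) self-report and/or from clinical records". The wording makes either source sufficient.

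Form S (Appendix C) sends a participant who was not admitted straight on to section 4. There, recurrent stroke and recurrent TIA are each a yes/no with a date, and MI has in addition a free-text explanation. An admission carries hospital, dates and an ICD code. Section 6, headed "Sources of Information related to death", asks where the information came from, but for deaths only.

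The standard for the index event is stricter. Form B item 1.3 requires a hospital physician's confirmation and adds: "Note: A GP is unable to confirm a stroke or TIA". Section 16 provides for checking diagnoses against medical records and/or by the study neurologists, in the context of recruitment.

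**The concern.** A patient-reported event is only as objective as the person reporting it. The trial is open-label to participants. Improving awareness of stroke symptoms is one of the aims that section 11 sets for coaching. Section 27 combines coaching with educational material, and section 24 adds information about a stroke-awareness app, which the assessment section describes as covering warning signs. If coached participants become readier to label a passing symptom as a TIA, the two arms report the same underlying events at different rates. Blinding the research assistants does not remove this, because the difference arises before the assistant hears of the event.

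At stake is the hazard ratio for CVD events. With few events expected, a handful of unverified TIAs could offset or reverse an apparent benefit. An analysis plan could not repair this later if the form does not record which events were confirmed.

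**Working it through.** **Entry standard against outcome standard**

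| | Index event | Non-fatal outcome event |
|---|---|---|
| Sufficient evidence | Hospital physician's diagnosis (Form B, 1.3) | Self-report (Table 1) |
| GP diagnosis enough? | No (Form B, 1.3) | Not addressed |
| Confirmation step | Records and/or study neurologists (section 16) | None stated |
| Source recorded | Form B screening is drawn from Clinical Portal | No field in Form S sections 3 to 7, except for deaths |

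The opening items of Form S, before section 3, were not in the text available, so the last row is limited to the part that can be seen. Heart failure is a named component but has no item in that part of Form S. Form F item 9.1 has a tick-box for it without an onset date, so it can be noted but not placed in time for a Cox model.

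**Illustration of size**

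The protocol states no expected event count or power for this comparison, so there is no figure to reproduce. What follows rests on assumptions.

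Inputs: up to 26% with new vascular events within four years (section 1); 180 per arm (Randomisation); a constant hazard (assumed); a true event ratio of 0.80 (assumed).

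- Yearly risk: 1 − (1 − 0.26)^(1/4) = 0.0725.
- Events per arm in a year without effect: 180 × 0.0725 = 13.05.
- Events under HWC at a ratio of 0.80: 0.80 × 13.05 = 10.44.
- Observed ratio with k extra self-reported TIAs under HWC: 0.80 + k/13.05. One extra gives 0.88, three give 1.03, five give 1.18.
- Chance alone: SE of the log ratio ≈ √(1/10.44 + 1/13.05) = 0.415, so the approximate 95% interval around 0.80 is 0.80 × exp(±1.96 × 0.415), about 0.35 to 1.81.

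Range over the yearly risk, with three extra TIAs:

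- 5% (9 events): 0.80 + 3/9 = 1.13.
- 10% (18 events): 0.80 + 3/18 = 0.97.
- 25% (45 events): 0.80 + 3/45 = 0.87.

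A second benchmark is the 11% reduction in major events that section 4 quotes for a 5 mm Hg fall, taken as a hazard ratio of 0.89. The number of extra events that would hide it is 180 × [p − (1 − (1 − p)^0.89)]. At p = 0.0725 this is 1.4 events; for p from 5% to 25% it is 1.0 to 4.3.

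Detecting 0.89 with 80% power needs about 4 × (1.96 + 0.84)² / (ln 0.89)² ≈ 2,312 events. With the counts above, the chance of a significant result in favour of HWC is only about 4% to 8%.

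**The case against.** The strongest reply has several parts.

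First, both arms have the same assessments at 3, 6, 9 and 12 months, made by research assistants blinded to arm, who also complete the event form. This is correct, and it removes one route of bias. It does not remove the participant's own labelling of symptoms.

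Second, symptom teaching is inferred. The session outline in section 24 lists none, and the awareness questionnaire and the Riskometer assessment are scheduled for both arms. Section 2's remark that "patients do not recognise TIA as a significant medical event" concerns perceived importance more than detection, and every participant has just had a diagnosed event. This weakens any claim about direction. Raised awareness nevertheless remains a stated aim of HWC.

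Third, the comparison has so little power that there is hardly a signal to distort. That is true of the test, but the estimate will still be reported, and so few events make it sensitive to one to three unverified reports.

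Fourth, confirmation would not remove differences in care-seeking, since better awareness may also bring more people to hospital. This stands and shapes the remedy.

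A reader might infer more than the text supports:

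- *That the comparison is biased against coaching.* Coached participants might also report more accurately, or under-report.
- *That contact frequency is an ascertainment difference.* Besides 12 sessions, "HWC participants will receive a short monthly telephone call from their coach to encourage maintenance of behaviour change", so HWC has about 4 + 12 + 6 = 22 contacts against 4. The extra contacts are with coaches, and the parts of the coach form that can be seen have no vascular event item.
- *That the safety monitoring counts are distorted in the same way.* A TIA without admission is neither a hospitalisation nor among the events listed as serious under Data Safety Management Committee.
- *That heart failure is found only through an admission code.* Form F has a tick-box for it; only the date is lacking.

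**Conclusion.** The point holds as a risk, not as a demonstrated bias. The rule that self-report suffices is stated, and it is looser than the trial's own entry standard. With unblinded participants and an intervention meant to raise symptom awareness, reporting can depend on arm. The exposure is mainly to TIAs without admission. Stroke and MI that lead to admission leave records and are much less affected.

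The size is illustrative only. The 26% is an upper figure that does not name TIA. The constant hazard sits badly with the adverse-outcome incidence of up to 25% within 90 days in the same section. The ratio of 0.80 and the numbers of extra TIAs are assumptions. Under them, three extra reports shift the ratio from 0.80 to 1.03, a shift well within chance variation.

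This concerns a secondary outcome. The primary endpoint is a measured blood pressure and is untouched. The change is worth making because it is cheap and must precede data collection to be of use, not because the trial's main conclusion depends on it.

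**What to change.** 1. In section 11 and Table 1, count a non-fatal CVD event only if it is confirmed in clinical records or by a study neurologist working without knowledge of arm. Treat self-report as a trigger to check.
2. Use the Clinical Portal access already in place in the same way and at the same times for both arms. Limit it to participants who have not withdrawn, because the Withdrawal section ends data collection at that point.
3. On Form S, add source and confirmation fields for each non-fatal event, and a heart failure item with a date.
4. Report two sensitivity analyses: one that adds events known from self-report only, and one on the composite without TIA. The second is needed because confirmation leaves differences in care-seeking in place.

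The cost is protocol and form wording, some record-checking time by staff who already have access, and somewhat fewer counted events because unconfirmed TIAs drop out of the main analysis.
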